#### 1.1.2 Number of Subjects

The study is planned to enroll approximately 80 subjects at approximately 5 centers in the United States.

## 1.2 Study Objectives

### 1.2.1 Safety Objective

The objective is to evaluate the safety of Sculptra Aesthetic as a single regimen for correction of Nasolabial Fold (NLF) contour deficiencies

 Title **Statistical Analysis Plan 43USSA1705 - New label** Doc id **MA-39345**

2019-02-11 09:58

Effective date:

## Effective

Version: 1.0

### 1.2.2 Effectiveness Objective

The objective is to evaluate the effectiveness of Sculptra Aesthetic as a single regimen for correction of NLF contour deficiencies.

### 1.3 Effectiveness Assessments

For all assessments, baseline will be defined as the observation that is closest to but prior to study treatment on Day 1. Likewise, change from baseline will be calculated as the value at a given time point minus the baseline value.

### 1.3.1 [REDACTED] Scale (

The **FRG** is a validated photograph-based outcome instrument that is designed specifically for quantifying facial folds.

88

Page 10 of 10

Comorbidity	Percentage
Hypertension	~10%
Diabetes	~25%
Coronary artery disease	~35%
Stroke	~30%
Chronic kidney disease	~45%

For more information, contact the Office of the Vice President for Research and Economic Development at [contact] or [[contact]](mailto:[contact]).

•

2019-02-11 09:58

Effective date:

**Effective**

Version: 1.0

[REDACTED]	[REDACTED]

[REDACTED]	[REDACTED]
[REDACTED]	[REDACTED]

### 1.3.5 Subject Diary

A subject diary will be dispensed to all subjects for daily completion for 28 days beginning on the injection day for each treatment with direct questioning for [REDACTED]

[REDACTED]	[REDACTED]

## 1.4 Effectiveness Endpoints

### 1.4.1 Primary Effectiveness Endpoint

Change from baseline on both sides of the face as assessed by the Blinded Evaluator using [REDACTED] at 48 Weeks after the first treatment session.

	
Title Statistical Analysis Plan 43USSA1705 - New label
	
Doc id MA-39345

--	--	-----------------------------------

#### 1.4.2 Secondary Effectiveness Endpoints

Secondary effectiveness endpoints include:

- Change from baseline on both sides of the face as assessed by the Blinded Evaluator using [REDACTED]
- Response to treatment using the [REDACTED] Scale ( [REDACTED] at Weeks 16, 24, 32, 40 and 48. [REDACTED]  
[REDACTED]  
[REDACTED]
- [REDACTED]: Nasolabial Folds Questionnaire at Baseline and at Weeks 24, 32, 40 and 48.
- Subject satisfaction score [REDACTED] Weeks 16, 24, 32, 40 and 48.
- [REDACTED]  
[REDACTED]

#### 1.5 Safety Assessments

The methods for collecting safety data are described in Section 7 of the Clinical Study Protocol.

#### 1.6 Safety Endpoints

Safety endpoints include:

- Incidence, intensity, time to onset, and duration of adverse events collected throughout the study period.
- Incidence, intensity, time to onset and number of days of pre-defined expected post-treatment events collected using subject diaries for 28 days from each treatment.
- [REDACTED]  
[REDACTED]

## 2 Statistical Methods

### 2.1 General Methods

Any change made to the finalized SAP before database lock will result in a SAP amendment. Otherwise, the change will be documented in the Clinical Study Report (CSR).

Some of the analyses detailed here may be more explicit or in some aspects different from those stated in the protocol. In case of differences, this SAP supersedes the statistical sections in the protocol.

For the study to be deemed successful, the following criteria need to be met:

- The primary effectiveness endpoints (change from baseline in [REDACTED] at Week 48 as assessed by the Blinded Evaluator) should be statistically significantly  $< 0$  on both sides of the face in the treatment group

 GALDERMA	Title Statistical Analysis Plan 43USSA1705 - New label	Doc id MA-39345
--	--	---------------------------

- The confidence intervals around the point estimates of the primary effectiveness endpoints in the treatment group should overlap with those of the reference group
- Acceptable safety profile in the treatment group.

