#### 2.4.3 Primary Effectiveness Analysis

For the 8 mL treatment groups the mean change from baseline in [REDACTED] as assessed by the Blinded Evaluator at Week 48 (denoted as  $\mu$ ) will be evaluated using a one-sided Student's t-test. Thus  $H_0: \mu \geq 0$  will be tested against  $H_1: \mu < 0$  in the right and left side of the face separately. In other words; the null hypothesis of no mean change in [REDACTED] (or possibly a worsening) as compared with baseline will be tested against the alternative hypothesis of an improvement from baseline in [REDACTED]. The test will be performed at the 2.5% significance level. Both right and left sides of the face will need to be statistically significantly less than 0 for the treatment to be judged effective. Results will include one-sided p-values and two-sided 95% confidence intervals for the mean change from baseline for both treatment groups. In order to confirm that there are comparable treatment effects in the two groups, there should be an overlap of the confidence intervals. A figure of these confidence intervals will be given.

As a sensitivity analysis, the above will be repeated using only randomized subjects.

Further, separate summaries and analyses will be created for each skin type and for each site. Consistency across skin types and sites will be explored by using an analysis of variance model. Separate models will be run with effects for 1) treatment, skin type, and treatment by skin type interaction, and 2) treatment, site, and treatment by site interaction.

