### 2.7 Determination of Sample Size

In the pivotal study report on which PMA P030050 Supplement 2 was based, [REDACTED] was used for effectiveness assessment. The change from baseline in [REDACTED] at Month 9 post treatment (which should approximately correspond to Week 48 in the current study, in case all four treatments are done) was -0.74 in the Sculptra group and the standard deviation was 0.57. However, the primary effectiveness endpoint was calculated differently in the pivotal study; the median of the left and right averages from three different evaluators was used. Since no averaging or use of the median of different measurements is done in the current study, the standard deviation is expected to be larger than in the pivotal one. Hence a standard deviation of 1 is assumed for these sample size calculations. Furthermore, with an assumed population change from baseline of -0.74, 90% power and one-sided test at the 2.5% significance level, at least 22 subjects are needed. With a drop-out rate of 15% at Week 48, at least 26 will need to be included to the treatment group. However, it was judged that 60 subjects would need to be included to the treatment group in order to provide a reasonable amount of safety data.

For the reference group, the rationale for sample size is based on effectiveness only. With 17 evaluable subjects, the study is adequately powered (80% power using a one-sided test at the 2.5% significance level) to detect a statistically significant change from baseline in [REDACTED] at Week 48, using the same assumptions for standard deviation and change from baseline as for the treatment group. With a drop-out rate of 15% at Week 48, at least 20 subjects need to be included to the reference group.

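### Overlap of two separate 95% confidence intervals cannot show that 8 mL and 5 mL have comparable effects: a significantly worse 8 mL result can pass and a clearly better one can fail

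*SAP*

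**What the plan says.** SAP 2.1 lists three criteria for a successful study: a significant improvement from baseline on both sides of the face in the 8 mL group, an acceptable safety profile, and, between these, "The confidence intervals around the point estimates of the primary effectiveness endpoints in the treatment group should overlap with those of the reference group".

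SAP 2.4.3 gives the purpose of the overlap criterion: "In order to confirm that there are comparable treatment effects in the two groups, there should be an overlap of the confidence intervals". The intervals are computed separately for each group: "Results will include one-sided p-values and two-sided 95% confidence intervals for the mean change from baseline for both treatment groups". The efficacy test itself uses the 8 mL group alone, one-sided: "The test will be performed at the 2.5% significance level". The same section adds a condition that covers the two sides jointly: "Both right and left sides of the face will need to be statistically significantly less than 0 for the treatment to be judged effective".

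SAP 2.7 sizes each group for its own change from baseline. Of the 5 mL group it says: "For the reference group, the rationale for sample size is based on effectiveness only". The readable text gives no margin, no direction, and no interval for the difference between groups as a basis for this criterion.

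**The concern.** The protocol's objective is effectiveness after changed reconstitution and injection procedures, compared to the approved label. Overlap is the only effectiveness criterion that uses the 5 mL group, so any statement of comparability rests on it. The rule has three faults.

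- **It is too lenient.** Two 95% intervals can overlap while the difference between the means is clearly significant.
- **It rewards imprecision.** A smaller or noisier reference group widens its interval and makes overlap easier to obtain.
- **It has no direction.** An 8 mL interval lying wholly on the better side of the 5 mL interval also fails.

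The headline verdict can therefore be wrong either way, in a report that the protocol synopsis says will go into the regulatory submission for marketing application.

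**Working it through.** **Inputs.** From SAP 2.7: SD 1 ("Hence a standard deviation of 1 is assumed for these sample size calculations"), change from baseline -0.74, 60 subjects on 8 mL, 20 on 5 mL, and a pivotal-study SD of 0.57, used here as the lower end of the range. From SAP 2.4.2: missing values in the ITT analysis are set to baseline, so the ITT intervals use about 60 and 20 subjects. At 15% drop-out, observed cases would be about 51 and 17. A negative change is an improvement, so a positive 8 mL minus 5 mL difference means 8 mL is worse.

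**1. The plan's own figures.** SAP 2.7 states: "with an assumed population change from baseline of -0.74, 90% power and one-sided test at the 2.5% significance level, at least 22 subjects are needed". One-sample t-test power (noncentral t, effect 0.74, SD 1, one-sided 2.5%) is 91.1% at n = 22 and 81.7% at n = 17. Drop-out inflation gives 22/0.85 = 25.9, so 26, and 17/0.85 = 20. The stated sizes are reproduced. They concern change within a group only.

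**2. What overlap tolerates.** The intervals overlap while the observed difference is at most t(0.975, n1-1)·SD/√n1 + t(0.975, n2-1)·SD/√n2. A pooled two-sample t-test is significant beyond t(0.975, n1+n2-2)·SD·√(1/n1+1/n2).

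| SD, n (8 mL/5 mL) | Overlap limit | Significant beyond | Two-sided p at overlap limit |
|---|---|---|---|
| 1, 60/20 | 0.258 + 0.468 = 0.726 | 0.514 | 0.006 |
| 1, 51/17 | 0.281 + 0.514 = 0.795 | 0.559 | 0.006 |
| 0.57, 60/20 | 0.147 + 0.267 = 0.414 | 0.293 | 0.006 |

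At SD 1 and 60/20 the limit is 0.726/0.74 = 98% of the assumed effect. At SD 0.57 it is 0.414/0.74 = 56%. With fewer subjects (51/17) the limit rises, so the rule becomes easier to pass.

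**3. Significantly worse results that pass (60/20).**
- SD 1: 8 mL mean -0.30, interval -0.56 to -0.04; 5 mL mean -1.00, interval -1.47 to -0.53. The 8 mL group is significantly below zero and the intervals overlap. The difference is 0.70, SE √(1/60+1/20) = 0.258, 95% CI 0.19 to 1.21, p = 0.008 against 8 mL.
- SD 0.57: 8 mL mean -0.37 (-0.517 to -0.223); 5 mL mean -0.74 (-1.007 to -0.473). Again both criteria are met, with p = 0.014 against 8 mL.

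**4. How often.** Simulation with normal data, 60/20, true 5 mL mean -0.74, assumed left-right correlation 0.7, both sides required:

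| True 8 mL effect | SD 1 | SD 0.57 |
|---|---|---|
| Half kept (-0.37): both effectiveness criteria met | about 65% | about 48% |
| Half kept: criteria met and 8 mL significantly worse on at least one side | about 16% | about 29% |
| Better by 0.37: study fails on overlap | about 15% | about 52% |

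At SD 1, a product that keeps two thirds of the effect (-0.49) meets both criteria in about 88% of trials. One better by 0.50 or 0.74 fails on overlap in about 30% or 66%. Cutting the reference group from 20 to 10 raises both-side overlap at half effect from about 85% to 90%.

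**5. Randomized subjects only.** Protocol 4.1 randomizes about 64 subjects 2:1, so about 43 and 21. At SD 1 the overlap limit is 0.763, against 0.532 for significance. The sensitivity analysis in SAP 2.4.3 repeats the same rule and inherits the fault.

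**The case against.** The strongest objection is that the 65% figure overstates the fault of the overlap rule itself. Most of those passes are trials in which a direct test would not have detected the deficit either. At SD 1 and half effect, a rule requiring no significant inferiority on either side would still pass 49% of trials. This stands: much of the leniency comes from a 20-subject reference group, and the share that pass while significantly inferior on at least one side is about 16% (SD 1) to 29% (SD 0.57). It also shows that the group is too small to confirm comparability by any rule, so it does not rescue the wording.

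Other points have partial force.

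- The requirement that 8 mL beat zero does screen out poor results, and the simulated rates already include it. It tests 8 mL against zero, not against 5 mL. It also largely masks the effect of halving the reference group, which barely changes overall success.
- A two-sided rule suits an aim of comparability, and any equivalence rule would fail a much better product. The gains of 0.50 and 0.74 are large against an assumed effect of 0.74. Even so, nothing in the plan says that a better 8 mL result should make the study unsuccessful.
- The plan includes ANOVA models with a treatment term, and shows both intervals in a figure. The models explore consistency across skin types and sites and are not success criteria. A figure of two intervals leaves the reader to approximate the difference.
- Protocol 10.4 and 10.11 cannot be read and might contain a rationale. SAP 2.1 says the SAP supersedes the protocol's statistical sections, and SAP 2.1, 2.4.3 and 2.7 are readable on this point.

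**Conclusion.** The concern holds and must be fixed. At SD 1 and 60/20, any observed 8 mL deficit between 0.514 and 0.726 is statistically significant and still satisfies the overlap criterion. At SD 0.57 the band is 0.293 to 0.414. These bands are arithmetic and need no assumption about correlation or margin. The pass and fail rates do rest on assumptions: normal data, left-right correlation 0.7 and a true 5 mL mean of -0.74, without modelling the zeros that baseline carried forward would add. Across SD 0.57 to 1, a product that has lost half the effect meets both effectiveness criteria in about 48% to 65% of trials, and one better by 0.37 fails on overlap in about 52% to 15%. The sample sizes in SAP 2.7 are correct for within-group change and do not support a comparability claim.

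**What to change.** In the second criterion of SAP 2.1 and in SAP 2.4.3, replace the overlap rule with the estimated 8 mL minus 5 mL difference in mean Week 48 change, for each side, with a two-sided 95% confidence interval. Take it from an ANCOVA with baseline score and site in the randomized subjects, so that the 16 non-randomized 8 mL subjects do not enter the comparison. They remain in the within-group analysis. State the conclusion as the largest 8 mL deficit that the upper limit excludes, and remove the wording that overlap confirms comparable effects.

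If a pass/fail rule is kept, make it one-sided on that upper limit, so that a better 8 mL result cannot fail, against a margin justified and fixed before any by-arm data are seen. SAP 2.6 lets the unblinded sponsor analyze data before completion. If by-arm results have already been seen, keep to estimation.

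**Cost.** An SAP amendment before database lock, which SAP 2.1 provides for, and one model per side on data already collected. No extra subjects are needed for the estimation version. The claim becomes weaker: the unadjusted half-width at SD 1 is 0.51 with 60/20 and 0.53 with 43/21. Against an illustrative margin of 0.37 (half of 0.74, since the documents give none), with no true difference and SD 1, power is about 30% with 60/20 and 26% with 51/17. At SD 0.57 it is 71% with 60/20. For 90% power at that margin with SD 1 and 3:1 allocation, about 412 evaluable subjects would be needed. The trial can estimate the difference but, at its planning SD, is unlikely to prove tight comparability.

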### 2.1.1 Programming Conventions

EMB Statistical Solutions will have responsibility for performing analyses. All computations for statistical analyses will be performed using SAS® software, Version 9.4 or later. All SAS programs used in the production of statistical summary outputs will be validated with independent programming prior to finalization. In addition, all program outputs will be independently reviewed. The validation process will be used to confirm that all data manipulations and calculations were accurately done. Once validation is complete, a senior statistical reviewer will perform a final review of the documents to ensure the accuracy and consistency with this plan and consistency within tables. Upon completion of validation and quality review procedures, all documentation will be collected and filed by the project statistician or designee.

The eCRF data for all subjects will be provided in Standard Data Tabulation Model (SDTM) datasets. Analysis Data Model (ADaM) datasets will be developed from the SDTM datasets for use in table and figure production.

### 2.1.2 Reporting Conventions

The formats for the tables, listings, and figures described in this SAP will be provided in a companion document. Changes to the formats of these reports that are decided after the finalization of the SAP will not require an amendment. In addition, any additional supportive or exploratory analyses requested after SAP approval will not require amendment of the SAP. These additional analyses will be described in the CSR.

All study data from the eCRFs as well as derived variables will be provided in subject data listings. An indication of specific listings for each data type will not be indicated in the text of subsequent SAP sections. Data listings supplied as part of the CSR will be sorted by study center number concatenated with subject number, assessment dates, and/or time point.

The following conventions will be applied to all data presentations and analyses:

- Quantitative variables will generally be summarized by the number of subjects, mean, standard deviation, median, minimum, and maximum. Unless otherwise specified, the minimum and maximum values will be displayed to the same number of decimal places as the raw data, the mean and median will be presented to one extra decimal place compared to the raw data, and the standard deviation will be displayed to two extra decimal places compared to the raw data
- Categorical variables will be summarized by the number and percentage of subjects (and number of events where appropriate) within each category. Unless otherwise specified, the percentage will be presented in parentheses to one decimal place. Frequency and percentage values of 0 will be presented as '0' rather than '0 (0)'.
- All summary tables will include the analysis population sample size (i.e. number of subjects).
- Date variables will be formatted as ddMMYY YYYY for presentation.

 GALDERMA	Title Statistical Analysis Plan 43USSA1705 - New label	Doc id MA-39345
--	--	---------------------------

2.1.3 [REDACTED]

## 2.2 Analysis Populations

The statistical analyses will be performed based on the following subject populations.

[REDACTED] Sensitivity analyses will include only randomized subjects (Section 2.4.3 and Section 2.5.2).

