4.1 General outline

This is a 48-week, randomized, evaluator-blinded, parallel-group, multi-center, study to evaluate the safety and effectiveness of treatment with Sculptra Aesthetic for correction of NLF contour deficiencies after changes in reconstitution and injection procedures compared to the approved label.

Approximately 64 subjects requiring correction of NLFs will be enrolled and randomized in a 2:1 ratio to treatment with Sculptra Aesthetic reconstituted with 8 mL of SWFI (treatment group) or to Sculptra Aesthetic reconstituted with 5 mL of SWFI (reference group). In addition, eight (8) subjects with FST IV and eight (8) subjects with FST V-VI will be included but not randomized. These subjects will be treated with Sculptra Aesthetic reconstituted with 8 mL of SWFI. When these numbers of FST IV-VI have been treated, any additional FST IV-VI will be randomized in a 2:1 ratio (8 mL:5 mL).

Approximately 60 subjects will be treated with Sculptra Aesthetic reconstituted with 8 mL of SWFI and a reference group of approximately 20 subjects will be treated with Sculptra Aesthetic reconstituted with 5 mL of SWFI as according to the current label.

[REDACTED]

Investigator blinding will be accomplished by using a Treating Investigator to administer the

 GALDERMA	<small>Title</small> 43USSA1705 Sculptra Clinical Study Protocol	<small>Doc id</small> MA-37876
---	--	--

Effective date: 2019-02-21 18:33

treatments and a Blinded Evaluator, to whom randomization and treatment are concealed, to conduct the blinded assessments. In addition, the Blinded Evaluator should not be allowed to retrieve study supplies or be present during the opening of the study supplies or injection procedure. All documents with information regarding study products and randomization assignment should be kept in a separate binder not available to the blinded evaluator. Safety assessments will be performed by non-blinded personnel.

Eligible subjects randomized to receive treatment will be injected by the Treating Investigator at Day 1. The method of injection is at the discretion of the treating Investigator according to Sections 2.2 and 6.6.

Sufficient amount of product should be injected to achieve optimal correction of the NLFs, in the opinion of the Treating Investigator and subject.

Information will be collected about treatment procedure (e.g. injection technique, depth, injection volume, needle sizes, and anesthesia used).

*Effective*

Version: 5.0

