#### 2.5.4 Subject Diary Symptoms

Diary data will be presented for each diary separately. The number and percentage of subjects reporting each pre-defined, expected, post-treatment symptoms, as collected in the 28-day diary, will be presented in total and by maximum severity. Number of days with the event will be presented by treatment group and category: 1, 2-7, 8-14, and 15-28.

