#### 2.5.5 Other Safety Analyses

Nodules and papules assessments will be summarized.

Device deficiencies and vision function assessments will be listed.

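### In the visible SAP, the randomised-only repeats stop short of the diary and nodule/papule tables, where about 27% of the 8 mL column is non-randomised FST IV-VI subjects

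*SAP*

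**What the plan says.** **Who is in each group.** Protocol 4.1 has a randomised part: "Approximately 64 subjects requiring correction of NLFs will be enrolled and randomized in a 2:1 ratio to treatment with Sculptra Aesthetic reconstituted with 8 mL", the remainder receiving 5 mL. It then adds: "In addition, eight (8) subjects with FST IV and eight (8) subjects with FST V-VI will be included but not randomized". Their treatment is fixed: "These subjects will be treated with Sculptra Aesthetic reconstituted with 8 mL of SWFI". Only after those places are filled are further FST IV-VI subjects randomised 2:1. The planned totals are about 60 on 8 mL and, for 5 mL, "a reference group of approximately 20 subjects will be treated with Sculptra Aesthetic reconstituted with 5 mL of SWFI".

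**How safety is tabulated.** SAP 2.2.3 puts every treated subject in the safety population, analysed as treated. SAP 2.5 summarises safety endpoints on that population by treatment group, descriptively and without inferential tests.

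**Where randomised-only analyses are planned.** SAP 2.2 reads "Sensitivity analyses will include only randomized subjects (Section 2.4.3 and Section 2.5.2". In SAP 2.4.3 the primary analysis is repeated. In SAP 2.5.2 the repeat follows directly after the AE overview and applies to it; the next paragraph treats the remaining AE tables separately.

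**Diary and nodules/papules.** SAP 2.5.4 gives incidence and maximum severity for each diary, and "Number of days with the event will be presented by treatment group and category: 1, 2-7, 8-14, and 15-28". SAP 2.5.5 says only "Nodules and papules assessments will be summarized". Neither section mentions randomised subjects or skin type. By-skin-type safety tables are visible only for product- or procedure-related AEs (SAP 2.5.2).

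**The concern.** The SAP already accepts that adding non-randomised subjects to one group calls for a check in randomised subjects: it plans one for the primary endpoint and one for the AE overview. The same reasoning applies to the diary events, which Protocol 3.1 and SAP 1.6 list as a safety endpoint. The AE overview cannot stand in for them, because Protocol 7.7.3 has the diary events assessed separately from AEs.

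The study asks what happens when reconstitution and injection procedures change, and it has a concurrent 5 mL group. Readers will set the 8 mL and 5 mL diary columns beside each other. By design those columns differ in reconstitution volume, in skin type mix and in whether all subjects were randomised. If event rates differ by skin type, part of any visible difference reflects who was enrolled. The randomised comparison sits in the same data but is not planned for these tables.

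**Working it through.** **1. Reproduce the planned group sizes (Protocol 4.1).**
- Randomised to 8 mL: 64 × 2/3 = 42.7.
- Randomised to 5 mL: 64 × 1/3 = 21.3 (stated: about 20).
- Non-randomised, all on 8 mL: 8 + 8 = 16.
- 8 mL total: 42.7 + 16 = 58.7 (stated: about 60).
- Overall: 58.7 + 21.3 = 80.

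The plan's figures reproduce. No sample size or significance level is in question.

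**2. Weight of the non-randomised subjects in the 8 mL column.** 16/58.7 = 27.3%, or 16/60 = 26.7% on the rounded total. In the 5 mL column it is 0%.

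**3. Effect on the 8 mL rate.** With *w* the weight from step 2:

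pooled 8 mL rate − randomised 8 mL rate = *w* × (rate in the 16 − rate in the randomised 8 mL subjects)

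The documents give no event rates, so the difference in brackets is assumed and shown over a range:

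| Assumed difference (points) | Shift, *w* = 16/60 | Shift, *w* = 16/58.7 |
|---|---|---|
| 10 | 2.7 | 2.7 |
| 20 | 5.3 | 5.5 |
| 30 | 8.0 | 8.2 |
| 50 | 13.3 | 13.6 |

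The sign is that of the unknown difference, so the pooled column could make 8 mL look better or worse.

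**4. If further FST IV-VI subjects are randomised.** Suppose 12 of the 64 are FST IV-VI, split 8 and 4. Their share is (16 + 8)/58.7 = 0.409 on 8 mL and 4/21.3 = 0.188 on 5 mL. For an assumed 30-point gap between FST IV-VI and FST I-III, the between-column shift is (0.409 − 0.188) × 30 = 6.6 points, compared with 8.2 when there are none.

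**5. Precision given up.** The 8 mL denominator falls from about 59 to about 43; the 5 mL denominator stays at about 21. At an assumed rate of 50% in both groups, the standard error of the difference is:
- pooled: √(0.25/59 + 0.25/21) = 12.7 points;
- randomised only: √(0.25/43 + 0.25/21) = 13.3 points.

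The small 5 mL group dominates both, so little precision for the contrast is lost.

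**The case against.** The strongest reply is that the plan makes no between-group safety claim for this mixing to bias. Safety is descriptive (SAP 2.5). The safety success criterion in SAP 2.1 concerns the 8 mL group alone. SAP 2.7 sizes the reference group on effectiveness only and chooses 60 on 8 mL for safety data. For describing 8 mL safety, pooling is the right primary table. All of this stands, and a reader who infers that a planned safety conclusion is invalid goes beyond the documents. What remains is that by-group tables are planned, and that the AE overview is equally descriptive yet gets a randomised-only repeat.

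Other tempting readings also fail:

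- *Particular visible skin reactions will make 8 mL look about 8 points better.* The diary items are redacted in SAP 1.3.5, and nothing visible says that reporting varies with Fitzpatrick type. The mechanism and the 30-point gap are assumptions.
- *The sentence in SAP 2.2 shows that no by-skin-type diary tables exist.* It concerns randomised-only analyses and says nothing about skin type.
- *The absence is proven.* Text before that sentence is redacted, SAP 2.5.3 is not visible, and Protocol 10.7 on subgroups has no visible body. The cross-reference naming only two sections makes a hidden provision unlikely but does not exclude it.
- *A randomised-only table would settle the effect of dilution.* With a standard error near 13 points, the 95% half-width is about 26. The table removes a built-in imbalance; it does not give a precise contrast.

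Finally, SAP 2.1.2 lets supportive analyses be added without an amendment. That is true, but such tables would not be pre-specified, and SAP 2.6 states that the sponsor is unblinded and may analyse data before completion.

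**Conclusion.** The point holds as a gap in the scope of the planned sensitivity analyses. On the visible text, the diary and nodule/papule tables set an 8 mL column that is about 27% non-randomised FST IV-VI subjects beside a 5 mL column with no guaranteed counterpart. A side-by-side reading of those descriptive tables is therefore not a randomised comparison.

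The size is about 0.27 times a rate difference that the documents do not give. Its direction is unknown, and it shrinks if further FST IV-VI subjects are randomised. The conclusion rests on three things: enrolment close to the planned 64 + 16; the nodule/papule summary following the by-group rule in SAP 2.5, since SAP 2.5.5 does not state its layout; and no contrary provision in redacted text. This is a cheap improvement rather than an error in a planned conclusion.

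**What to change.** - Add Sections 2.5.4 and 2.5.5 to the randomised-only sentence in SAP 2.2.
- Repeat the diary tables (incidence, maximum severity, number of days) and the nodule/papule summary in randomised subjects.
- State that any 8 mL versus 5 mL remark on these endpoints rests on the randomised-only tables, and keep the pooled tables to describe 8 mL safety.

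The cost is one SAP sentence and a few repeated tables, produced by putting a population filter on existing programs. The downside is the smaller 8 mL denominator in the repeated tables, about 43 instead of 59. Design and sample size do not change.
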